ALZUMAB™ should not be administered to patients having history of severe allergy or known hypersensitivity reaction to any component of ALZUMAB™ or any murine proteins. Additionally, ALZUMAB™ is contraindicated in patients with any active serious infection including tuberculosis and HIV-AIDS.

It is recommended that live/attenuated vaccines not be given concurrently with ALZUMAB™.

As with other IgG antibodies, itolizumab may cross the placenta during pregnancy. The available clinical experience is too limited to exclude a risk, and administration of ALZUMAB™ is therefore not recommended during pregnancy.

Infections and Reactivation of Tuberculosis

Physicians should exercise caution before and during Itolizumab Injection treatment in patients with a history of recurrent infections or underlying conditions which may predispose them to serious infections. Patients should be monitored closely for the development of signs and symptoms of infection during and after treatment with Itolizumab.

4. Objectives

Primary Objectives:

To study the efficacy and safety of adding Itolizumab in patients with Moderate to Severe COVID-19 complications (Cytokine Release Syndrome).

Secondary Objectives:

To study the effect of immunomodulation by Itolizumab and its correlation to clinical improvement by evaluating biomarker data (IL6, TNF-a, IL17, IL1, Interferon -A etc.) before and after Itolizumab treatment

5. Outcome Measures

Primary Outcome Measures:

1. Proportion of patients with deterioration of lung function as measured by*:
 - Stable SpO₂ without increasing FiO₂
 - Stable PaO₂ without increasing FiO₂
2. Reduction of endo-tracheal intubation rate, measured as rate of patients needing intubation*
3. Reduction in proportion of patients who need*
 - Non-invasive ventilation
 - Invasive mechanical ventilation
 - High flow nasal oxygen
4. Time of duration of mechanical ventilation or time to end of mechanical, measured as elapsed time from the start date of mechanical ventilation to the weaning date, for patients needing intubation*
5. One-month mortality rate between the two arms* [Time Frame: up to 1 month]

1-month mortality is defined as the ratio of patients who will live after 1month from study start out of those registered at baseline

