8.1 Schedule of Study Visits and Procedures

Visit	S1	W1	W2	W3	W4	End of Study
Weeks	-2 to 0	0	1	2	3	4 th week
Days	-14	1 [^]	8 [^]	15 [^]	22 [^]	30 [#]
Event						
Informed Consent	X					
Medical History	X					
Inclusion/Exclusion Criteria ^a	X					
Weight	X	X	X	X	X	X
Physical Examination, Vital signs ^{\$}	X	X	X	X	X	X
Hematology* [;] ^{\$}	X	X	X	X	X	X
Biochemistry** [;] ^{\$}	X	X	X	X	X	X
Chest X Ray/CT scan ##	X	X	X	X	X	
Randomisation	X					
Best Supportive Care		X	X	X	X	
Pre-medication @ in Arm A		X	X	X	X	
ALZUMAb infusion ^b		X	X	X	X	
Cytokines and Immunophenotyping assessment	X	X ^d				
PaO ₂ /FiO ₂ ratio	X	X	X	X	X	
CRP	X	X	X	X	X	X
Daily Morning SOFA Score ^c	X	X	X	X	X	
Concomitant medication check	X	X	X	X	X	X
Adverse events	X	X	X	X	X	X

[^] Window period: ± 48 Hours.

^a All inclusion / Exclusion criteria to be reviewed prior to first dosing. Screening period is up to 14 days however screening and baseline visit can happen in one day and screening assessment can be considered as baseline assessments.

^b 1.6 mg/kg dose iv infusion, if well tolerated and improvement in patient observed, investigator has the discretion to continue with 1.6 mg/kg dose every 2 weeks or 0.8 mg/kg weekly regimen in combination therapy with standard of care (anti-viral and antibiotic drugs). Subsequent dose and frequency can be modified, deferred or stopped if patient recovers as per investigator's

discretion. If patients' overall parameters improve (if performed and RT-PCR is negative) further dose need not be given. Total infusion received during study duration can vary from 1 to 4 for each patient. If patient recovers/is discharged earlier than 30 days, then patient should be contacted telephonically to get status of the patient on 30th day after enrolment.

c: Daily SOFA Scoring until patient moved out of ICU/equivalent, and later SOFA score frequency as per investigator discretion. If patient is not admitted in the ICU/equivalent at the time of enrolment, then it is recommended to capture these assessments daily for first 7 days.

Window period for assessment at 4th week or 30th day is \pm 3 days.

*Hematology assessments (blood test) include: hemoglobin, total leukocyte count, differential count, absolute neutrophil count, absolute lymphocyte count, and platelet count.

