## 3.2 Outcome Measures

### 3.2.1 Primary endpoint

1. Proportion of patients with deterioration of lung function as measured by\*:
  - Stable SpO2 without increasing FiO2
  - Stable PaO2 without increasing FiO2
2. Reduction of endo-tracheal intubation rate, measured as rate of patients needing intubation\*
3. Reduction in proportion of patients who need\*
  - Non-invasive ventilation
  - Invasive mechanical ventilation
  - High flow nasal oxygen
4. Time of duration of mechanical ventilation or time to end of mechanical, measured as elapsed time from the start date of mechanical ventilation to the weaning date, for patients needing intubation\*
5. One-month mortality rate between the two arms\* [ Time Frame: up to 1 month ] 1-month mortality is defined as the ratio of patients who will live after 1 month from study start out of those registered at baseline
6. Change in inflammatory markers like CRP (C-reactive protein) level, d-Dimer, ferritin etc. [ Time Frame: Arm A; baseline, during treatment (Before every dose and 12 to 24 h after every dose) up to 1 month, Arm B: baseline, 12 to 24 h and approx. 7 and 14 days after randomization ]

\* Applicable for both the arm

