## **9 Efficacy Evaluation**

### **Primary Efficacy Evaluation**

Proportion of patients with deterioration of lung function as measured by Stable SpO2 without increasing FiO2 and Stable PaO2 without increasing FiO2 will be summarized using count and

percentage. The difference between two proportion with its 95% Confidence interval and associated p-values may be presented, if p-value is less than 0.05 it can be concluded that there is a statistically significant difference between two proportions.

Reduction of endo-tracheal intubation rate, measured as rate of patients needing intubation will be summarize using descriptive statistics.

Reduction in proportion of patients who need/ Non-invasive ventilation / Invasive mechanical ventilation/high flow nasal oxygen will be summarized using count & percentage.

One-month mortality rate between the two arms will be summarized. The difference between two rates with its 95% Confidence interval and associated p-values may be presented, if p-value is less than 0.05 it can be concluded that there is a statistically significant difference between two-rates.

Change in inflammatory markers like CRP (C-reactive protein) level, d-Dimer, ferritin etc will be summarize with descriptive statistics. Change from Baseline may be presented along with 95% CI.

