### **13 Programming Considerations, Listing of Tables, Figures & Format, Software detail**

All tables, data listings, figures (TLFs), and statistical analyses will be generated using SAS® for Windows, Release 9.4 (SAS® Institute Inc., Cary, NC, USA) or any other validated statistical software. One SAS program will be used to create several outputs / a separate SAS program will be created for each output. Output files will be delivered in Word / pdf format.

For few assessments (weight, physical examination, vital signs haematology, biochemistry Chest X Ray/CT scan), screening assessments will be considered as baseline assessment (as day 1).

Missing data:

All attempts will be made to collect all data per protocol. Any data point that appears to be erroneous or inexplicable based on clinical judgment will be investigated as a possible outlier. If data points are identified as outliers, sensitivity analyses may be performed to examine the impact of including or excluding the outliers. Subjects who meet fatal outcome during the observing period up to 30 days will be an event. Subjects lost to follow up or withdraw consent during the observing period, will be censored at last assessment. Patient data will be censored at the time of their last observed assessment in case of lost to follow up, withdrawal consent or after 30 days of enrolment.

Following Rules may be applied for the derivation of efficacy endpoints

- Patients who discharged from hospital (with improvement, Off O2), the status at discharge will be carried forward.
- Patients who lost to follow up will be considered as Non evaluable (NE)
- Patients who worsen or met fatal outcome, status at event will be carried forward.

Note: Telephonic improvement of weaning of O2 will be considered as improved.

These rules will be applied to analyse following endpoint:

Proportion of patients with deterioration of lung function as measured by:

- Stable SpO2 without increasing FiO2
- Stable PaO2 without increasing FiO2

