### 14.2.7 One-month Mortality Rate

	Arm A [n (%)]	Arm B [n (%)]
Number of patients died	XX (XX.X %)	XX (XX.X %)
95% CI Difference between Rate	XX (XX , XX)	
p-value	XX	

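### The primary outcome one-month mortality is defined as the proportion alive, while the planned table and event rule count deaths; its time origin and denominator also need a single definition

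*SAP*

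**What the plan says.** **Definition.** SAP 3.2.1 item 5 reads: "1-month mortality is defined as the ratio of patients who will live after 1 month from study start out of those registered at baseline". Protocol section 5, Primary Outcome Measures, item 5, has the same sentence: "1-month mortality is defined as the ratio of patients who will live after 1month from study start out of those registered at baseline".

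**Table.** SAP Table 14.2.7 has a row "Number of patients died", followed by "95% CI Difference between Rate" and a p-value row. It states no time origin.

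**Inference.** SAP section 9 says of mortality: "The difference between two rates with its 95% Confidence interval and associated p-values may be presented". No test is named.

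**Event and censoring.** SAP section 13, under missing data: "Subjects who meet fatal outcome during the observing period up to 30 days will be an event". Patients are censored at their last observed assessment "in case of lost to follow up, withdrawal consent or after 30 days of enrolment".

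**Follow-up.** Protocol 8.1, footnote b, asks for a telephone status check on the 30th day after enrolment for patients who recover or are discharged earlier. A separate footnote reads "Window period for assessment at 4th week or 30th day is" plus or minus 3 days. The schedule marks randomisation in the screening column, before the Day 1 column.

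**Who is counted.** SAP section 7 limits the ITT/FAS set in Arm A to patients who received at least one full dose; in Arm B, randomisation is enough. Protocol section 6 and SAP 4.5 treat an Arm A patient without one full infusion as not randomised and reuse the code for the next patient at that site.

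**The concern.** Mortality is the hardest of the six primary outcomes. It is also one of only two for which SAP section 9 describes a between-arm difference with a confidence interval and p-value. Its definition is the complement of its name. A programmer working from SAP 3.2.1 and one working from Table 14.2.7 would report opposite signs for the same endpoint, and under the written definition a drug that prevents deaths raises mortality.

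The same sentence leaves two further parts of the endpoint unsettled: the day from which the month is counted, and the patients in the denominator. With about 20 and 10 patients, one death is 5 points in Arm A (1/20) and 10 points in Arm B (1/10), so a rule that moves one patient in or out is visible in the result.

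**Working it through.** The plan has no formal sample-size calculation and assumes no death rate, so there is no figure of its own to reproduce. The check is a comparison of texts plus an illustration.

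**1. Direction.**

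| Place | What is counted |
|---|---|
| Protocol 5 item 5; SAP 3.2.1 item 5 | Patients alive |
| SAP Table 14.2.7 | Patients who died |
| SAP 13, missing data | Death up to 30 days is the event |

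The definition stands alone against the two places that say how to compute the result.

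**2. Size of the reversal.** Inputs: about 30 patients at 2:1 (Protocol section 6, SAP 4.5), so 30 × 2/3 = 20 in Arm A and 30 × 1/3 = 10 in Arm B. The death counts are assumed: 3 in each arm.

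- Deaths: 3/20 = 15% and 3/10 = 30%. Difference = 15 - 30 = -15 points.
- Alive: 17/20 = 85% and 7/10 = 70%. Difference = 85 - 70 = +15 points.
- Standard error, the same on both scales because p(1 - p) is symmetric: √(0.15 × 0.85/20 + 0.30 × 0.70/10) = √0.027375 = 0.1655. The 95% half-width is 1.96 × 0.1655 = 0.324.
- 95% CI: -47.4 to +17.4 points on deaths, -17.4 to +47.4 points on alive.
- Two-sided Fisher exact p: 0.372 on both scales.
- Risk ratio: 0.15/0.30 = 0.50 on deaths, 0.85/0.70 = 1.21 on alive. It crosses 1 and also changes in size.

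Other assumed counts show the same pattern:

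| Deaths A/20 v B/10 | Difference, deaths | Difference, alive | Fisher p (both) | Risk ratio, deaths / alive |
|---|---|---|---|---|
| 1 v 2 | -15 | +15 | 0.251 | 0.25 / 1.19 |
| 2 v 3 | -20 | +20 | 0.300 | 0.33 / 1.29 |
| 2 v 4 | -30 | +30 | 0.141 | 0.25 / 1.50 |
| 3 v 5 | -35 | +35 | 0.078 | 0.30 / 1.70 |

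The label, sign and any ratio measure change. The p-value and interval width do not.

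**3. Origin.** The definition counts from the start of the study, a term neither document explains. Read as the trial's calendar start, it cannot work for patients who enter later. Read as the patient's own start, it is undefined. SAP 13 and the Protocol telephone check both count from enrolment. Visit days count from Day 1, and randomisation is scheduled in the column before it, although screening and baseline may fall on one day. The randomisation date and Day 1 can therefore differ.

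**4. Denominator.** The definition divides by patients registered at baseline. The ITT/FAS set leaves out Arm A patients without one full dose and has no such condition in Arm B. To illustrate with assumed figures: if 21 patients are allocated to Arm A, one does not complete the first infusion and dies, and 3 of the other 20 die, mortality is 3/20 = 15.0% in ITT/FAS and 4/21 = 19.0% among all allocated.

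**5. Day 30 window.** Plus or minus 3 days allows an assessment from Day 27 (30 - 3). If the window is also applied to vital status, a contact on Day 27 to 29 stands in for status at Day 30. Table 14.2.7 is a simple count and percentage, and no rule says how a patient censored before Day 30 enters it.

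**The case against.** The best defence is that nobody would compute the sentence literally. The endpoint's name, Table 14.2.7 and the event rule all say death, and Table 14.2.9 lists alive, dead and unknown separately. The two-sided p-value is the same either way. This stands as a limit on the consequence: the table makes a reversed report unlikely. It does not excuse a primary endpoint whose only definition, in both documents, contradicts its own table.

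A reader might infer more than the documents support:

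- **That a significance conclusion could flip.** It cannot: two-sided p and interval width are the same on both scales. Nor is the p-value a firm commitment, since SAP 9 makes it optional, although the table has a row for it.
- **That the month could shift by up to 14 days through screening.** No text uses screening as the mortality origin.
- **That SAP section 8 sets a different clock in each arm,** first dose in Arm A and randomisation in Arm B. That section defines baseline values, not the start of mortality follow-up.
- **That the origin contradicts the planned table.** The table states no origin. The mismatch is with the censoring and follow-up text, and if the patient's own start is meant, it is ambiguity rather than contradiction.
- **That deaths between Day 27 and Day 30 will be missed.** Early-discharged patients already have a status call set for the 30th day. Whether the 3-day window also covers that call is unclear. Appendix 3 of the Protocol requires on-study deaths to be recorded, and Listing 16.1.17 holds the date of death and the last date known alive.

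**Conclusion.** The direction error is definite and rests on no assumption: a primary outcome called mortality is defined as the proportion alive, while its table and event rule count deaths. Taken literally, it reverses the sign of the difference (-15 against +15 points with 3/20 v 3/10 assumed deaths) and moves a ratio to the other side of 1. It leaves two-sided significance and precision unchanged.

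The undefined origin and the denominator mismatch are real but secondary. Their size depends on how many patients have different randomisation and Day 1 dates, and on how many Arm A patients do not complete a first infusion; the documents give neither number. The Day 30 window is a smaller point and holds only if that window is applied to vital status. The sentence should be corrected before analysis.

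**What to change.** In Protocol section 5 item 5 and SAP 3.2.1 item 5, replace the defining sentence with:

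*One-month mortality = number of patients who died from any cause within 30 days after the date of randomisation, divided by all patients allocated to that arm, including Arm A patients who did not complete a first full infusion.*

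Three changes go with it:

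- State that the 30 days run from the randomisation date in both arms, not from Day 1 of the visit schedule, and bring the enrolment wording in SAP 13 and Protocol 8.1 into line.
- Reconcile the denominator with the replacement note (Protocol section 6, SAP 4.5) and the ITT/FAS definition (SAP section 7). Without this, an Arm A patient who is treated as not randomised could still drop out of the count.
- State that vital status is confirmed on or after the 30th day, for example by telephone 30 to 33 days after randomisation.

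If a proportion alive is also wanted, list it separately under the name survival.

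Cost: a later phone call for some patients, vital-status follow-up of replaced Arm A patients, and consistent edits to the sections named above. Listing 16.1.17 already has the fields for date of death and last date known alive.

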### 3.2.2 Secondary endpoints

1. Biomarkers (IL-6, TNF-a, IL1, IL17, etc...) [ Time Frame: Arm A; baseline, during treatment (Before every dose and 12 to 24 h post dose) up to 1 month, Arm B; baseline, 12 to 24 h and approx. 7 and 14 days after randomization ]
2. Lymphocyte count [ Time Frame: Arm A; baseline and before every dose up to 1 month, Arm B; baseline, approx. 7 and 14 days after randomization ] Lymphocyte count assessed by routinely used determination of blood count
3. PaO2 (partial pressure of oxygen) / FiO2 (fraction of inspired oxygen, FiO2) ratio (or P/F ratio) [ Time Frame: Arm A; baseline, during treatment (Before every dose and 48 h post dose) up to 1 month, Arm B: baseline, 48 h and approx. 7 and 14 days after randomization] calculated from arterial blood gas analyses (values from 300 to 100)
4. Number of participants with treatment-related side effects as assessed by Common Terminology Criteria for Adverse Event (CTCAE) version 5.0 [ Time Frame: during treatment and up to 30 days after the last treatment dose ]\* graded according to CTCAE criteria (v5.0)
5. Radiological response [ Time Frame: at baseline, after seven days and if clinically indicated (up to 1 month) ]\* Thoracic CT scan or Chest XR
6. Duration of hospitalization [ Time Frame: from baseline up to patient's discharge (up to 1 month) ]\* Days of hospitalization and ICU

7. Remission of respiratory symptoms [ Time Frame: up to 1 month ]\* time to independence from non-invasive mechanical ventilation calculated in days
8. Remission of respiratory symptoms [ Time Frame: up to 1 month ]\* time to independence from oxygen therapy in days

\* Applicable for both arms

## **4 TRIAL DESIGN AND DESCRIPTION**

### **4.1 Trial Design**

It is a Multi-Centric, Open label, Two Arm Randomized, Pivotal Phase 2 Trial to Study the Efficacy and Safety of Itolizumab in COVID-19 complications. Patients who have tested positive for virological diagnosis of SARS-CoV2 infection (PCR) are planned to be randomised for enrolment from various centres in India. All eligible patients entering into the study will be randomized in 2:1 ratio to receive the treatment A/ B respectively.

### **4.2 Subject Selection**

Patients who have tested positive for virological diagnosis of SARS-CoV2 infection (PCR) are planned to be randomised for enrolment from various centres in India.

### **4.3 Inclusion Criteria**

1. Male or female adults above 18 years (not tested in children yet)
2. Informed consent for participation in the study
3. Confirmed virological diagnosis of SARS-CoV2 infection (RT-PCR)
4. Hospitalized due to clinical worsening of COVID-19 infection
5. Oxygen saturation at rest in ambient air  $\leq 94\%$
6. Patients who are in moderate to severe ARDS as defined by PaO2/Fio2 ratio of < 200 or more than 25% deterioration from the immediate previous value.
7. Baseline serum ferritin level  $\geq 400$  ng/mL or IL-6 levels greater than 4 times ULN, if known

Note: Either of Inclusion number 6 or 7 is required for inclusion of the patient into the study. Since there is logistical delay in getting results in time, biomarker data as inclusion criteria may be used if already known.

### **4.4 Exclusion Criteria**

1. Known severe allergic reactions to monoclonal antibodies
2. Active tuberculosis (TB) infection
3. History of inadequately treated tuberculosis or latent tuberculosis

Note: Latent tuberculosis should be excluded based on history, physical examination and chest x ray before dosing (day 1). QuantiFERON TB also should be performed, however considering criticality of patient condition, patient can be dosed without QuantiFERON TB test results. If

QuantiFERON TB test is positive, then continuation of patient in the study is investigator's discretion considering benefit-risk evaluation with the sponsor.

4. In the opinion of the investigator, progression to death is highly probable, irrespective of the provision of treatments
5. Patient on invasive mechanical ventilator support.
6. Have received oral anti-rejection or immune-suppressive drugs within the past 6 months  
Note: Patient receiving oral anti-rejection or immune-suppressive drugs regularly in the last 6 months will be excluded. Patient will be included if received short course of steroids.
7. Participating in other drug clinical trials like using anti-IL-6 therapy like tocilizumab (participation in COVID-19 anti-viral trials may be permitted if approved by Sponsor)
8. Patient on treatment of anti-IL-6 or plasma therapy as a part of supportive care
9. Pregnant or breastfeeding, or positive pregnancy test in a pre-dose examination
10. Any serious medical condition or abnormality of clinical laboratory tests that, in the investigator's judgment, precludes the patient's safe participation in and completion of the study
11. Patients with known history of Hepatitis B, Hepatitis C or HIV
12. Absolute Neutrophils count (ANC) <1000 / mm^3
13. Platelet count <50,000 / mm^3
14. Absolute Lymphocyte count (ALC): <500/mm^3

Note: ANC, ALC and platelet counts can be done in local lab in the hospital.

#### **4.5 Sample Size, Treatment Assignment, Randomization**

Approximately 30 patients are considered sufficient to explore the study objectives and will be included in this study (number of patients may be increased if there is benefit observed in initial cohort of patients. There is no formal sample size calculation estimated). All eligible patients entering into the study will be randomized in 2:1 ratio to receive the treatment A/ B respectively. A computer derived randomization schedule is planned to be generated using appropriate system e.g. SAS to assign patient to treatment groups. Randomization will be central and appropriate system (e.g. remote telephone based, computer-based email, sealed envelope) will be used to distribute randomization schedule to the site Note: If the patient is randomised to Arm A and is not initiated itolizumab or not administer one full infusion, is then not considered randomized. The same randomisation code will be used for the subsequent subject in that particular site.

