Source data is all information, original records of clinical findings, observations, or other activities in a clinical study necessary for the reconstruction and evaluation of the study. Source data are contained in source documents. Examples of these original documents, and data records include: hospital records, clinical and office charts, laboratory notes, memoranda, subject's diaries or evaluation checklists, pharmacy dispensing records, recorded data from automated instruments, copies or transcriptions certified after verification as being accurate and complete, microfiches, photographic negatives, microfilm or magnetic media, x-rays, subject files, and records kept at the pharmacy, at the laboratories, and at medico-technical departments involved in the clinical study.

Location of Data

All records and documents pertaining to the study will be maintained in the permanent files of the Investigator and will be available for inspection by the authorized party at any time.

Statistical Analysis

In general, continuous variables is summarized using descriptive statistics such as mean, standard deviation, 95% confidence interval (CI), minimum, and maximum. Categorical variables are summarized using proportions (counts and percentages). All statistical tests will be performed at 5% level of significance (two-sided test) and p-value<0.05 considered statistically significant (if necessary). All statistical analysis will be performed using SAS® (version 9.4 or higher) system software (SAS Institute Inc., USA)/or R/or EAST/or NCSS software.

11.Administrative Procedures

Ethics and Good Clinical Practice

This research will be carried out in accordance with the clinical research guidelines established by the basic principles defined in the revised New Drugs and Clinical Trials 2019, India and the principles enunciated in the Declaration of Helsinki [Ethical Principles for Medical Research Involving Human Subjects, revised, October 2013]. The investigator is responsible for overall activities at the center in accordance with Indian ICH-GCP guidelines, current New Drugs and Clinical Trials 2019 and ethical guidelines for biomedical research on human subjects issued by ICMR.

Interim study report - Data will be provided to DSMB (constituted prior to first patient screened) on a periodic basis. Based on DSMB recommendation, interim clinical study report may be prepared and submitted to DCGI/regulatory agencies.

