## **11 Interim Study Report**

Data will be provided to DSMB (constituted prior to first patient screened) on a periodic basis. Based on DSMB recommendation, interim clinical study report may be prepared and submitted to DCGI/regulatory agencies.

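### Enrolment can grow on undefined observed benefit and interim reports can go to the regulator, while the p<0.05 conclusion rule is not confined to one analysis, so the error rate can exceed 5%

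*SAP*

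**What the plan says.** On size, SAP 4.5 states: "Approximately 30 patients are considered sufficient to explore the study objectives". It adds: "There is no formal sample size calculation estimated". Patients are "randomized in 2:1 ratio to receive the treatment A/ B respectively", so about 20 in Arm A and 10 in Arm B. The same paragraph allows growth: "number of patients may be increased if there is benefit observed in initial cohort of patients". Protocol section 6 (planned number of subjects) has the same sentence. Neither document says which endpoint shows benefit, how large it must be, when the initial cohort ends, how far enrolment may rise, or who decides.

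On interim data, SAP 11 states: "Data will be provided to DSMB (constituted prior to first patient screened) on a periodic basis". It continues: "Based on DSMB recommendation, interim clinical study report may be prepared and submitted to DCGI/regulatory agencies". Protocol section 11 has the same text. The number and timing of reviews and the content of an interim report are not given.

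On inference, the Primary Efficacy Evaluation in SAP 9 says of one-month mortality: "if p-value is less than 0.05 it can be concluded that there is a statistically significant difference between two-rates". It gives a parallel sentence for the lung-function proportions. The protocol's Statistical Analysis paragraph (section 10) sets a two-sided 5% level for all tests, where testing is necessary. SAP 4.1 describes the trial as open label and pivotal.

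Neither document contains an interim boundary, an allocation of alpha over time, a combination test, or an estimate adjusted for a data-driven extension.

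**The concern.** Three permissions combine. Enrolment can be enlarged because the results look good. A report can go to the regulator before the end. The only rule for drawing a conclusion is an unadjusted p<0.05, with no statement of when it applies. Because the trial is open label, results by arm are not masked from those who might decide to enlarge it.

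Followed as written, the plan leaves three occasions for a positive claim: at about 30 patients, in an interim report, and after an enlargement prompted by a favourable first cohort. If more than one is used, the chance of a false claim exceeds the stated 5%. If the added number is picked after seeing the data, even a single final test is no longer protected. In a trial that was extended because it looked favourable, the pooled estimate also carries the selected first-cohort result with it. A regulator reading a p-value from such a trial could not tell what error rate stands behind it.

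**Working it through.** **Plan's own figure.** There is none to reproduce. The 5% level is an input, and no power, effect size or error calculation is given.

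**Inputs from the documents.** N about 30, 2:1 (20 and 10); two-sided 0.05, critical value 1.96; periodic review; enlargement on observed benefit.

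**Assumptions, because the documents are silent.** Two to four looks; enlargement to 60, 90 or 120; benefit meaning a first-cohort statistic z1 above 0, 0.5 or 1; a normally distributed test statistic; no true effect.

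**1. Unadjusted 0.05 at equally spaced looks, claim allowed at any.** The statistics at looks j<k have correlation √(j/k), so for 30 then 60 it is √(30/60) = 0.71. The error is 1 − P(|z| ≤ 1.96 at every look).

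| Looks | Two-sided error |
|---|---|
| 2 | 8.3% |
| 3 | 10.7% |
| 4 | 12.6% |

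**2. Claim at 30, or after a benefit-triggered extension.** The pooled statistic is zf = (z1√30 + z2√(N−30))/√N. The benefit-side error is P(z1 > 1.96) + P(c < z1 ≤ 1.96 and zf > 1.96), where c is the trigger. For N of 60 to 120 and c of 0 to 1 this is 3.5% to 4.3%, against 2.5%. For example, N=90 and c=0 gives 4.3%; N=120 and c=1 gives 3.5%.

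**3. The same extension to a fixed N, with one final test.** The benefit-side error is P(z1 > c and zf > 1.96), because an unextended trial has z1 below the trigger and cannot be significant for benefit. This is 1.4% to 2.5% over the same grid, and 4.0% to 5.0% two-sided. There is no inflation.

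**4. Added number chosen freely from the data, one final test.** The worst case, one-sided, is α + exp(−z²/2)/4 = 0.025 + exp(−1.96²/2)/4 = 0.025 + 0.1465/4 = 0.0616, or 6.2%.

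**5. Binary endpoint with an exact test.** With 20/10 then 40/20, Fisher's test at both looks and event rates of 10% to 40%, the two-sided error is 3.5% to 5.7%. An uncorrected chi-square test in the same setting gives 6.6% to 8.5%. The SAP names no test.

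**6. Estimate, no true effect, extension to 60 when z1>0.**
- Given z1>0, the mean of z1 is 0.798 SE (SE at N=30). Pooled with an equal unbiased second stage it halves to 0.399. In units of the SE at N=60 that is 0.399 × √2 = 0.56 upward.
- Averaged over extended and unextended trials: 0.5 × 0.399 + 0.5 × (−0.798) = −0.20 SE (SE at N=30), which is downward.

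**7. Interim threshold of p<0.001.** With one to three interim looks and a final test at 0.05, the total two-sided error is about 5.0% to 5.1%. At 20 against 10 this threshold is very strict under Fisher's test: 5/10 control events against 0/20 gives p = 252/142,506 = 0.0018, and 6/10 against 0/20 gives 210/593,775 = 0.00035.

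**The case against.** The strongest reply is that the plan schedules no interim test. P-values are optional throughout, the size is described as enough to explore, and an interim report might contain no inference. A reader might infer that p<0.05 will be applied at every look. The documents do not say so. What they do is leave it open, and an interim study report with no rule of its own has only the SAP 9 rule to follow. The pivotal label and the wording that a difference can be concluded make it hard to treat every p-value as merely exploratory.

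A reader might also infer that enlarging on observed benefit raises the error by itself. Step 3 shows that it does not when the final size is fixed and there is one final test. Nor is the effect estimate inflated in general: the upward bias holds only among extended trials, and on average under no effect it is downward.

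The size of the inflation rests on assumed looks and extension sizes, and on a normal test used with 20 and 10 patients. With Fisher's test little of it remains. These limits stand, and they make the point conditional. They do not supply the missing rule.

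**Conclusion.** The concern holds in conditional form. The plan does not show that its type I error is controlled, because it permits enlargement on undefined benefit and interim reporting while leaving the p<0.05 conclusion rule open to repeated use. The error exceeds 5% if a claim may be made both at about 30 patients and after enlargement, or if the added number is chosen from the data.

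Under the stated assumptions and a normal test, the two-sided error is about 8% to 13% for two to four unadjusted looks. The one-sided error is 3.5% to 4.3% for a claim at either stage of a benefit-triggered extension, and at most 6.2% for a freely chosen extension with one final test. Upward bias of about 0.56 SE applies to a trial extended to 60 on z1>0 with no true effect. It does not describe all trials run under the plan. This should be corrected: the gap is real, its consequence depends on how the permissions are used, and closing it is cheap.

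**What to change.** In SAP 4.5 and 11, and in the matching text of protocol sections 6 and 11, state:

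- There is one enlargement decision, made by the DSMB at about 30 patients, to a second-stage size fixed in advance.
- Interim reports are descriptive and carry no efficacy conclusion, or carry one only at p<0.001. At 20 against 10, that threshold comes close to a ban.
- First-cohort and second-stage results are shown separately beside the pooled result.

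In SAP 9, state that the p<0.05 conclusion rule applies once, at the final analysis. This fixes the occasion only; which endpoint and visit carry the conclusion must still be named.

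If the second-stage size cannot be fixed in advance, prespecify an inverse-normal combination of the two stages with weights set beforehand. With a fixed size it adds nothing to error control and can be left out.

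The cost is a few sentences in the SAP, which SAP 1 allows to be revised before database lock, and a short protocol amendment. The sponsor gives up any interim efficacy claim at p between 0.001 and 0.05. The final threshold stays at 0.05.
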